Clinical Institute Withdrawal Assessment of Alcohol Scale, Revised	Measure of current alcohol withdrawal symptoms	X		
Blinding Questionnaire	One question assessing knowledge of condition		X	

**Primary Drinking Outcome.** The *Form 90* (Miller, 1996) is a semi-structured interview that gathers daily calendar-based alcohol and illicit drug use data. A 2-month assessment window will be used at each of the time-points. The *Form 90* will be used to derive estimates of the primary outcome: drinks per drinking day. The *Form 90* has demonstrated reliability in the collection of alcohol and drug use data (Maisto, Conigliaro, Gordon, McGinnis, & Justice, 2008; Sobell, Brown, Leo, & Sobell, 1996).

**Weekly During Treatment Measures.** An abbreviated assessment battery will be administered weekly during treatment to assess state mindfulness (Toronto Mindfulness Scale (Lau et al., 2006)), mindfulness practice in the prior week, craving (PACS; Flannery Volpicelli, & Pettinati, 1999), negative urgency and lack of planning items from the UPPS (Littlefield et al., 2015; Whiteside & Lynam, 2001), and negative affect (Short Forms of Anger, Sadness, Stress from NIH Emotions Toolbox; Salsman et al., 2013).

**Behavioral Tasks.** All behavioral tasks will be completed via computer during EEG to provide a measure of electrical brain activity during rest and completion of the tasks. To examine inhibitory control, we will use a *Stop Signal Task* (Logan, Van Zandt, Verbruggen, & Wagenmakers, 2014) in which participants make left-right judgments of the directionality of an arrow presented on the screen. For each trial, a circle will appear for 500 ms, followed by a left or right-pointing arrow for up to 1 second, and between 500 ms and 2500 ms jittered inter-trial interval to reduce anticipatory responses. Approximately 25% of trials will be "stop trials" with a tone played to signal participants to inhibit the

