#### IV. *Unanticipated Problems/Adverse Events*

We would terminate the study if we found there were significant unanticipated adverse consequences for participation. For example, we would terminate the study if we found statistically significant preliminary results indicating that participants receiving the active tDCS were drinking at a higher rate than those in the sham condition. Analyses to compare sham versus active tDCS treatment efficacy will be conducted in February 2018, after a sufficient number of subjects have been treated, and at the time of submitting our annual progress report to NIH, which will occur in June 2018. We would also terminate the study if we became aware of any publications with such findings in other studies. Any unanticipated problems or adverse events will be reported to the IRB promptly and within 7 days of occurring.

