## II. *Data Analysis/Statistical Considerations*

**Power analysis and sample size considerations.** We conducted power analyses using effect sizes from a pilot study ( $d=0.64$  and  $d=0.43$  on drinks per drinking day at post- and 2-month follow-up). With desired power  $>0.80$ , a two-tailed  $\alpha < 0.05$ , and three time-points, we will need 70 participants to detect a medium effect of active tDCS + MBRP vs. sham tDCS + MBRP on drinks per drinking day at follow-up. For mediation analyses we will need 74 participants to detect a medium effect. Attrition of 15% is anticipated based on our pilot tDCS study and thus we propose to recruit  $n=86$  participants to allow for some attrition. We anticipate screening up to 350 participants in order to recruit a sample of 86 participants.

**Data Analyses and Missing Data.** The primary study aim is to test the overall efficacy of the active tDCS + MBRP intervention compared to a sham tDCS + MBRP group. We will use maximum likelihood estimation for all analyses, which provides the variance-covariance matrix for all available data and is the preferred method for estimation when some data are missing. Variables associated with missing data and those used in randomization (gender, age, treatment history) will be covaried in all analyses.

**Aim #1: Efficacy Analyses.** All assessment data will be analyzed for outliers and missing cases to detect any bias that might result from differential attrition. The efficacy of active tDCS + MBRP versus sham tDCS + MBRP will be examined using a generalized linear mixed model with drinks per drinking day at the end of treatment and follow-up as the primary outcomes. We hypothesize active tDCS will be associated with significantly larger reductions in drinks per drinking day following treatment, as compared to sham tDCS. Interim analyses to compare sham versus active tDCS treatment efficacy will be conducted in February 2017, after a sufficient number of subjects have been treated, and at the time of submitting our annual progress report to NIH, which will occur in June 2017.

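### The interim active-versus-sham looks are dated a year apart in two sections, and two visits are primary with no rule saying which contrast decides the trial

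*Combined protocol and SAP*

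**What the plan says.** **Interim looks.** Section II (Data Analysis/Statistical Considerations), Aim #1: "Interim analyses to compare sham versus active tDCS treatment efficacy will be conducted in February 2017", and again with the annual report to the funder in June 2017. Section IV (Unanticipated Problems/Adverse Events): "Analyses to compare sham versus active tDCS treatment efficacy will be conducted in February 2018", and again with the annual report in June 2018. Section IV times the first look "after a sufficient number of subjects have been treated" and Aim #1 uses the same condition; neither gives a count. Section IV also states a consequence: "we would terminate the study if we found statistically significant preliminary results indicating that participants receiving the active tDCS were drinking at a higher rate" (the comparison is with sham). It attaches no numerical level to that criterion.

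**Primary test.** Aim #1 specifies a generalized linear mixed model "with drinks per drinking day at the end of treatment and follow-up as the primary outcomes". Hypothesis 1 (Objectives/Aims) names both visits, joined by a plain conjunction. Other wording is singular: "The primary study aim is to test the overall efficacy" opens the analysis paragraph, and in Section V the Form 90 "will be used to derive estimates of the primary outcome: drinks per drinking day". The power paragraph says "we will need 70 participants to detect a medium effect" and refers to follow-up. It is the only place where two-tailed 0.05 appears.

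**The concern.** The two sections describe the same comparison under the same conditions but a year apart. Section IV links the looks to terminating the study, so the conflict decides when the harm check happens and on how much data.

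One mixed model can yield an end-of-treatment effect, a 2-month effect, an average over visits, or a group-by-time test. If the deciding term is not fixed in advance it can be picked after the results are known, and the false-positive rate then depends on the pick. The pilot effects in the power paragraph differ by visit (d = 0.64 and 0.43), so the choice also changes power a good deal.

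**Working it through.** **1. Dates, side by side**

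| | Section II, Aim #1 | Section IV |
|---|---|---|
| First look | February 2017 | February 2018 |
| Second look | June 2017 | June 2018 |
| Trigger for first look | sufficient number treated | sufficient number treated |
| Stated use | listed under efficacy | termination for harm |

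Both are current text, not an amendment log. The matching months, trigger and report point to one schedule with a year changed in one place.

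**2. Can the plan's N = 70 be reproduced?** Stated inputs: medium effect, two-tailed 0.05, power above 0.80, three time-points. Not stated: the within-person correlation ρ and the contrast. I take a medium effect as f = 0.25 or d = 0.5.

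- Between-group repeated-measures F test with m visits: λ = N f² m / [1 + (m − 1)ρ], on 1 and N − 2 df. With m = 3, the smallest N giving 80% power is 62, 70, 78 and 86 for ρ = 0.2, 0.3, 0.4 and 0.5. At N = 70 and ρ = 0.3, λ = 70 × 0.0625 × 3 / 1.6 = 8.20 and power is 0.806.
- The same test on the two post-baseline visits only (m = 2): 78, 84, 90 and 98 for the same ρ.
- Group-by-time test, m = 3: 44, 38, 34 and 28.
- ANCOVA on the mean of the two post-baseline visits: N = 4(1.96 + 0.84)²/d² × [(1 + ρ)/2 − ρ²]. At d = 0.5 and ρ = 0.3 this is about 125.6 × 0.56 = 70.
- Single visit, two-sample t test, d = 0.5: 128 in total; 70 gives 54% power.

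Two different contrasts reach 70, each only with an unstated ρ of 0.3. The figure therefore does not identify a contrast.

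**3. Error rate under two primary visits.** The visit statistics are taken as bivariate normal with no true difference, each visit tested at ±1.96, and assumed correlation r.

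- Either visit suffices: 1 − P(|Z₁| < 1.96 and |Z₂| < 1.96).
- Both in the same direction: 2 × P(Z₁ < −1.96 and Z₂ < −1.96).

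| r | Either, two-sided | Either, benefit direction | Both, same direction |
|---|---|---|---|
| 0.3 | 9.5% | 4.8% | 0.5% |
| 0.5 | 9.1% | 4.5% | 0.9% |
| 0.7 | 8.4% | 4.2% | 1.7% |
| 0.9 | 7.0% | 3.5% | 3.0% |

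One named contrast gives 5% two-sided and 2.5% in the benefit direction.

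**4. The looks.** A stop only for harm can remove trials from the set that reaches a final benefit claim and cannot add any. The false-benefit rate therefore stays at no more than 2.5%.

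**5. Power by contrast (illustrative).** Completers: 86 × 0.85 = 73.1, so 73, or 36.5 per arm with equal allocation assumed. The calculation is a two-sample t test with pilot effects and equal SDs, not the planned mixed model. The effect on the average is d = [(0.64 + 0.43)/2] / √[(1 + r)/2], which gives 0.664, 0.618, 0.580 and 0.549 for r = 0.3, 0.5, 0.7 and 0.9.

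- End of treatment alone: 77%.
- 2 months alone: 44%.
- Average of both: 80%, 74%, 69% and 64% for the same r.

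With an assumed correlation of 0.5 between baseline and each visit, these become 88%, 55% and 77–95%. The 95% end is implausible: it needs the two later visits to correlate less with each other (0.3) than with baseline (0.5). Baseline drinking is not among the covariates listed by name in Section II, so its handling matters too.

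**The case against.** The strongest reply is that a single mixed model and a singular aim already imply one test, that Hypothesis 1 most naturally requires an effect at both visits, and that the only stated consequence of a look is a harm stop. On that reading nothing is inflated: requiring both visits gives 0.5–3.0%, and harm-only looks leave the benefit error alone. The date clash is then an editorial slip.

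Much of this stands. The text provided does not say that success at either visit is enough, so 7.0–9.5% is what one permitted reading would cost, not the plan's established error rate. The singular primary outcome in Section V names a measure, not a number of tests. The reply still does not identify the deciding term: a both-visits rule, an average and a follow-up effect are all consistent with some of the wording, and they give different answers.

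A reader might also infer that the looks inflate the false-positive rate. If benefit could be claimed at 0.05 at either of two looks or at the end, the two-sided rate would be about 9–11% under assumed look timings. No section says benefit can be claimed at a look, so that figure is not a finding. Nor does the text establish four separate looks, although it does not strictly exclude them.

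**Conclusion.** The concern holds in two parts. First, the current text contradicts itself by a year on when the comparison tied to stopping for harm is made; this needs no assumption. Second, two visits are primary with no deciding contrast, no either-or-both rule and no multiplicity rule in the text provided. One section next to the adverse-events section was not available, so nothing is claimed about its content.

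The size of the second part depends on the rule eventually used: 7.0–9.5% two-sided if either visit suffices, 0.5–3.0% if both must succeed in the same direction. Both ranges assume 0.05 per visit and a visit correlation of 0.9 to 0.3.

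It is tempting to read N = 70 as showing that an averaged effect was intended, or as an error. Neither follows. The number cannot be reproduced without an unstated correlation and contrast. The F-test route that gives 70 uses three time-points; on the two post-baseline visits alone it needs 84 at the same correlation.

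**What to change.** 1. Reconcile Sections II and IV to one interim schedule. State that the looks serve only the existing harm check and that no benefit is claimed at a look. If efficacy looks are intended, give error-controlled levels for the looks and the final test. No harm threshold is proposed here.
2. Before unblinded data are seen, fix one primary test at two-sided 0.05, as one of:
   - a single named contrast from the mixed model, for example the treatment effect averaged over the two post-baseline visits with baseline drinks per drinking day as a covariate;
   - an explicit rule that both visits must be significant;
   - a multiplicity adjustment, if success at either visit is to count.
3. Report the remaining visit effects as secondary.

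The cost is text only, with no new data or visits. The downside is that a benefit seen at only one visit may become secondary evidence. Under the pilot effects with 73 completers, the unadjusted average has 64–80% power, against 77% for end of treatment alone and 44% for 2 months alone. It falls 8 and 13 points below end of treatment at visit correlations of 0.7 and 0.9. Splitting alpha to 0.025 per visit would also cost power: with 74 completers, from 79% to 70% at d = 0.64 and from 46% to 35% at d = 0.43.

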### *VII. Study Location(s)*

Assessments and intervention sessions will take place in the Psychology Clinical Neuroscience Center in Logan Hall, Department of Psychology, University of New Mexico. Data analysis will be done at Logan Hall, Department of Psychology, University of New Mexico in offices maintained by PI [name].

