### **Personnel Resources**

All study staff will be trained in recognizing signs and symptoms of intoxication as well as withdrawal symptoms. The UNM Psychology Department is located less than 1 mile away from several hospitals, including the UNM Hospital Emergency Department. The PI is a licensed clinical psychologist with extensive experience in the prevention and treatment of substance use disorder. The PI will train and supervise research staff and the study therapists to utilize data provided at each assessment point as well as clinical judgment to monitor and evaluate the condition of participants.

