#### I. *Data Management Procedures and Confidentiality*

Online surveys and data collection forms have been used in our previous studies, and will be re-tested prior to utilization. Data are monitored on a daily basis during the baseline period to track response rates, evaluate success of the randomization procedure for producing equivalent groups, and assess data quality. Data are monitored on a weekly basis during each follow-up assessment period. Data cleaning is minimal because COINS has safeguards in place to minimize data entry errors. All data will be inspected continuously throughout the trial by a RA who is familiar with potential problems with data acquisition. All data will be double-checked by two independent persons. Scoring syntax that was developed for our prior studies will be used to produce summary variables, and standard procedures will be utilized for dealing with missing data.

We have taken a number of measures to ensure the confidentiality and integrity of the data and the safety of the participants. As described in the protections for human subjects sections above, all data from the proposed study will be identified by a numerical ID code only, which will be assigned during the phone screening. After phone screening, the phone screening form will be destroyed for those who are not eligible, although first and last names will be recoded to prevent re-screens and the demographic information and reasons for ineligibility for those who are ineligible will be recorded in a separate document without identifiers for reporting purposes. For eligible individuals the phone screening form will be de-identified and only linked to the participant with the participant ID code. The information linking the numerical participant ID code to identifying information will be maintained separately in a locked filing cabinet and kept separate and secure from the de-identified. All identifying information will be stored in a separate encrypted and password protected file and will not be linked with the screening or assessment data. At the conclusion of the study, the list linking the ID code to identifying information will be destroyed. Further, a Certificate of Confidentiality, which provides additional protection against obligatory release of confidential information, will be obtained from the Department of Health and Human Services.

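### The two mid-trial active-versus-sham efficacy comparisons produce more by-arm information than the harm-stopping rule needs, with no stated limit on who runs or sees them

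*Combined protocol and SAP*

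**What the plan says.** Under Data Analysis/Statistical Considerations, Aim #1, the combined protocol and SAP states: "Interim analyses to compare sham versus active tDCS treatment efficacy will be conducted" in February 2017, and places a second look "at the time of submitting our annual progress report to NIH, which will occur in June 2017". The section on Unanticipated Problems/Adverse Events describes what appears to be the same pair a year later: "Analyses to compare sham versus active tDCS treatment efficacy will be conducted in February 2018", then again with the progress report in June 2018.

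The adverse-events section is the only place that ties a decision to these looks: the study would be terminated if preliminary results showed significantly more drinking in the active arm. No action for benefit, for futility or on sample size is given in either section.

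Four other parts of the document bear on the point:

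- Study Location(s): "Data analysis will be done at Logan Hall, Department of Psychology, University of New Mexico in offices maintained by PI".
- Personnel Resources: "The PI will train and supervise research staff and the study therapists". The General Protections paragraph repeats this.
- Data Collection Procedures describes the tDCS sessions as double blinded, with both conditions mixed within every treatment group.
- Primary Drinking Outcome: drinks per drinking day comes from the Form 90, a semi-structured interview. The only listed check on the blind is a single question to participants after treatment.

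**The concern.** A harm rule needs one answer at each look: is the active arm significantly worse, yes or no? What is scheduled is a comparison of efficacy, which also yields the direction and size of any benefit while groups are still being treated. Nothing in the available text keeps that result from the people who deliver treatment, supervise it or collect the outcome.

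If the team learned which arm was ahead, this could influence recruitment, retention effort or the way later Form 90 interviews are probed. A positive final result on an interviewer-collected outcome would then be open to a challenge that the plan could easily have prevented.

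**Working it through.** **1. The plan's own numbers.** The document gives 74 participants for mediation, 70 for the main comparison, 15% attrition and a target of 86.

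- From 74: 74 × 1.15 = 85.1, rounded up to 86, which matches. 74 / 0.85 = 87.06, rounded up to 88.
- From 70: 70 × 1.15 = 80.5, rounded up to 81. 70 / 0.85 = 82.4, rounded up to 83. Neither gives 86.

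The expected number analysed is 86 × 0.85 = 73.1, taken as 73, or 36.5 per arm if allocation is equal (an assumption).

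**2. What each possible decision needs, against what the plan provides.**

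| Decision at an interim look | In the plan? | By-arm information needed |
|---|---|---|
| Stop for harm (active drinking more) | Yes, adverse-events section | Criterion met or not met |
| Stop for benefit | No | None |
| Stop for futility | No | None |
| Change sample size | No | None |

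The scheduled output is wider than the one decision requires.

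**3. Is the harm look a real use?** Yes, though a weak one. Take half of the 70 participants (17.5 per arm), one time-point and a true harm of d = 0.5. The noncentrality is 0.5 × √(17.5/2) = 1.479, so power is Φ(1.479 − 1.96) ≈ 0.32. With no true difference and a critical value of 1.96 at each of two looks, simulation gives a chance of wrongly meeting the criterion of about 0.038 to 0.041. That range covers assumed information fractions of 0.5 and 0.75, 0.33 and 0.67, or 0.25 and 0.5. The plan states neither the fractions nor the critical value.

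**4. How much could operational bias matter?** No document figure gives its size, so this is a sensitivity calculation only. Suppose knowledge of the interim result shifts reported drinking by δ SD in favour of active, in a fraction f of participants. The average shift is fδ, and

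λ = fδ × √(36.5/2) = fδ × 4.272

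Rejection rate = Φ(−1.96 + λ) + Φ(−1.96 − λ)

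| f | δ | fδ | λ | Two-sided false-positive rate |
|---|---|---|---|---|
| 0 | – | 0 | 0 | 5.0% |
| 0.25 | 0.1 | 0.025 | 0.107 | 5.1% |
| 0.25 | 0.2 | 0.05 | 0.214 | 5.5% |
| 0.5 | 0.1 | 0.05 | 0.214 | 5.5% |
| 0.5 | 0.2 | 0.10 | 0.427 | 7.1% |
| 1 | 0.1 | 0.10 | 0.427 | 7.1% |
| 1 | 0.2 | 0.20 | 0.854 | 13.7% |

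The f = 1 rows are an upper limit that the design cannot reach, because participants already assessed at the time of the look cannot be affected by it. The calculation uses a normal approximation for one time-point, not the planned mixed model.

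**The case against.** The strongest reply has several parts.

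- **The looks have a purpose.** A reader might infer that they put the blind at risk for nothing. The documents do not support that: the dated analyses follow closely on the termination rule and evidently serve it. This part stands, and the harm check should be kept.
- **Access is not documented.** A reader might infer that the PI or staff see unmasked by-arm results. The text says where data analysis in general is done and whom the PI supervises. It does not say who sees interim results or whether labels are masked. Some text after the adverse-events section was also unavailable to this review, so the lack of a firewall or monitoring body is known only for the text at hand. What remains is that nothing available prevents access.
- **An overall direction does not reveal an individual's allocation.** Both arms sit in the same groups with the same therapist, so general encouragement and recruitment changes reach both. Differential probing or retention effort needs a guess at the participant's arm. This largely stands, and it limits the plausible bias. It does not remove it: the reduced-current option at baseline is described only for the active condition and sensations are rated during sessions, so some clues may exist.
- **The NIH report.** A reader might infer that by-arm results go into it. The plan says only that the second look happens "at the time of submitting our annual progress report to NIH", which describes timing, not content.
- **Baseline monitoring.** The data-management section plans to "evaluate success of the randomization procedure for producing equivalent groups". A reader might count this as a further leak. It involves no post-treatment outcome, cannot show which arm is ahead, and helps detect a randomisation fault.

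**Conclusion.** The point holds as a matter of design and access control. Two efficacy comparisons by arm are scheduled mid-trial, the single decision attached needs only a yes-or-no harm answer, and the available text restricts neither who performs nor who sees them. The resulting risk of operational bias is avoidable.

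Its size is unknown. With half the participants assessed after the look (an assumption) and an assumed shift of 0.1 or 0.2 SD in that half, the false-positive rate goes from 5% to about 5.5% or 7.1%. A figure near 14% would need a 0.2 SD shift in everyone, including those already assessed, and should not be used. Nor do the documents show that the blind has been broken or will be.

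Separately, the two sections give different years for the same looks (2017 and 2018) and must be reconciled. The point above does not depend on which is meant. The change is worth making before any look takes place.

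**What to change.** In Aim #1 of Data Analysis/Statistical Considerations and in Unanticipated Problems/Adverse Events:

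1. Replace the interim efficacy comparison with a harm-only check in one direction (active worse than sham), using the harm criterion already in the plan.
2. Assign it to an existing person who has no participant contact, no therapist supervision and no outcome-interview role. That person must hold the arm key, because a directional rule cannot be evaluated without knowing which label is active.
3. State that only 'harm criterion met' or 'not met' goes to the PI and the team.
4. State that any drinking data in the NIH progress report are pooled across arms.
5. Reconcile the 2017 and 2018 dates.

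Leave the baseline balance checks in the data-management section as they are.

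The cost is a change of wording and the naming of one suitable person; the documents do not identify who that would be. No extra participants or visits are needed. The downside is that neither the team nor the funder sees drinking results by arm before the final analysis. If the team already works behind such a barrier, stating it in the two sections would settle the access question.
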